#### **21.4. Clinical Site Effect**

All revascularization surgeries will be performed by the same experienced neurosurgeon.

#### **21.5. Subgroup analysis**

All analysis of effect of revascularization surgery on outcomes by pre-specified subgroups will be conducted:

- ✧ Age
- ✧ Gender, men vs. women
- ✧ hypertension, yes vs. no
- ✧ diabetes, yes vs. no
- ✧ Smoking, yes vs. no
- ✧ Post infarction, yes vs. no
- ✧ Suzuki grade I, II, III, IV, V, VI
- ✧ Operation time
- ✧ BMI, <25, 25-30,  $\geq 30$  Kg/m^2
- ✧ Hypoperfusion (CTP, ASL),

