## **9. Enrollment of Patients**

All of Patients who meet the clinical criteria will undergo MRI, CTP and DSA. Patients with progressive stenosis or occlusion in the terminal portion of the internal carotid artery and/or the initial portion of the anterior or middle cerebral arteries unilaterally or bilaterally and formation of abnormal collateral networks (moyamoya vessels) at the base of the brain according to DSA, hypoperfusion based on perfusion CT or DSA and no significant new infarction lesions on MRI will be asked to participate and sign consent. Once this is completed, the patient will be enrolled and, if randomized to multimodal neuronavigation guiding precise bypass group, will undergo multimodal neuronavigation guiding precise bypass surgery after enrollment.

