## 10. Randomization of Patients

The central randomized method based on our own system. Patient who has signed the informed consent form and met all inclusion criteria without any exclusion item could be enrolled. Once the patient enrolled in the study, the system will automatically assign the study patient a random number with the exact group that he/she should be treated. Then the investigator should record this number and group in the original case history and the coming treatment record of the study patient. According to the protocol, this patient should be treated into the randomized group or the control group.

The investigator's team should archive the randomized list and the related documents (randomized application form) together in the trial folder, which clinical trial department of the site has to store.

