## 12. Multimodal Neuronavigation Procedure

**Pre-procedure:** All patients randomly assigned to both arms will be suspend aspirin 7 days before the revascularization procedure and restart taking aspirin on the first day postoperatively.

**Intra-procedure:** The surgical procedure will be done under the general anesthesia. ICG fluorescence angiography using Flow800 software and electromagnetic neuronavigation system is required during the procedure of revascularization. An

initial ICG fluorescence angiography will be performed when the dural membrane is unfolded to expose the blood vessels on the surface of the brain. According to the appearance order of vessels to assess the velocity of cerebral flow. Neuronavigation system is used to judge the cerebral hypoperfusion area under different recipient vessels. The vessel was chosen as the receptor with lower flow velocity and lower cerebral perfusion area to perform anastomosis.

Papaverine is used to prevent the occurrence of vasospasm. During surgery, the heparinized water was used to flush the donor's and the receptor's lumen for minimization of thrombosis or thromboembolism risk. An anastomotic end-to-side continuous (or intermittent) suture was performed using a 10-0 nonabsorbable vascular suture thread.

**Post-procedure:** Aspirin 100mg per day must be used for the entire duration of follow-up. Clopidogrel is not necessary after the surgery unless a cardiologist recommends taking clopidogrel for a cardiac indication.

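### Section 21.5 lists operation time, undefined and known only after randomization, as a treatment-effect subgroup, so that subgroup result is liable to bias

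*Protocol*

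**What the plan says.** Section 21.5 introduces its list with the statement that "All analysis of effect of revascularization surgery on outcomes by pre-specified subgroups will be conducted". Two entries matter here: "Operation time", which stands alone without definition, unit or cut-off, and "Suzuki grade I, II, III, IV, V, VI".

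On sequence, section 10 states that "Once the patient enrolled in the study, the system will automatically assign the study patient a random number" together with the group. Section 9 says that a patient allocated to guidance "will undergo multimodal neuronavigation guiding precise bypass surgery after enrollment".

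On content, the synopsis and section 5 define the guided arm by Flow800 and multimodal MR assessment used to choose the recipient vessel; the other arm is simply called empirical. Section 12 says that "ICG fluorescence angiography using Flow800 software and electromagnetic neuronavigation system is required during the procedure of revascularization". It adds that "An initial ICG fluorescence angiography will be performed when the dural membrane is unfolded" and that "Neuronavigation system is used to judge the cerebral hypoperfusion area under different recipient vessels", both before the anastomosis.

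Section 21.1 sets 50 patients per arm without a calculation and calls the trial exploratory. Section 21.3, however, mentions subgroup analysis in the same breath as confirmatory testing and makes no multiplicity adjustment.

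**The concern.** Randomization makes the arms comparable overall and within any group defined by what was known beforehand. It gives no such protection within groups defined by something that happens later and that the arm may alter. If guidance adds time, a long guided operation may be a routine case plus the guidance steps, while a long empirical operation is more often a hard case. Comparing the two mixes the effect of guidance with case difficulty.

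What is at stake is the credibility of one named subgroup result. It would carry the label pre-specified, and section 21.3 does not clearly mark subgroup results as exploratory. The Suzuki entry raises a different and smaller issue: grade is a baseline factor and the split is not biased, but six levels are many for a trial with few primary events.

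**Working it through.** The plan's only related figure, 100 patients, is stated without inputs, so there is nothing to reproduce.

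**Step 1: when is the variable known?** Allocation takes place at enrollment (section 10) and surgery after it (section 9). Duration of surgery, and equally its timing, is therefore known only after allocation.

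**Step 2: can allocation move it?** If duration is meant, section 12 places ICG angiography, reading of vessel order and navigation before the vessel is chosen. The synopsis and section 5 make these assessments the defining feature of the guided arm. A longer operation is a reasonable inference, but no section gives durations. If timing is meant, these steps do not shift it.

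**Step 3: what would a shift do?** This is an illustration; every input is an assumption. There is no treatment effect. Surgical difficulty raises duration (correlation 0.3, 0.5 or 0.7) and event risk (odds ratio 2 per SD; overall risk about 10.6%). Guidance adds d SDs of duration, and patients are split at the pooled median. Each scenario has 2,000,000 simulated patients. Ranges run over the three correlations.

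| d (SD) | Risk ratio, short stratum | Risk ratio, long stratum | Guided share of long stratum |
|---|---|---|---|
| 0 | 0.997 to 1.008 | 0.996 to 1.007 | 50% |
| 0.25 | 0.928 to 0.962 | 0.944 to 0.983 | 55% |
| 0.5 | 0.869 to 0.937 | 0.896 to 0.947 | 60% |
| 1 | 0.747 to 0.887 | 0.785 to 0.904 | 69% |

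The overall risk ratio stays between 0.995 and 1.009 throughout. The distortion arises only within strata, and only when allocation shifts duration.

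**Step 4: Suzuki grade and the primary endpoint.** The protocol's rates are 4% (30-day stroke per hemisphere, section 3), 10.1% (one-year death, TIA or stroke, section 3) and 15% (ceiling for perioperative stroke or death, section 15). None is the exact primary endpoint. Assume a hazard ratio of 0.5, approximated by halving the risk:

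- 4%: 50 × 0.04 + 50 × 0.02 = 3.0 events; divided by 6 = 0.5 per grade.
- 10.1%: 50 × 0.101 + 50 × 0.0505 = 7.6 events; divided by 6 = 1.3 per grade.
- 15%: 50 × 0.15 + 50 × 0.075 = 11.25 events; divided by 6 = 1.9 per grade.

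The averages per grade combine both arms and assume equal grade frequencies.

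A grade with no event in one arm has no finite, non-zero hazard ratio, and the Wald interval of section 21.3 is unusable there. Now take the more generous case of equal risk in both arms, that is 4, 10.1 or 15 events. By hand, at 15% with 50/6 = 8.33 patients per grade and arm, the chance of at least one event in a cell is 1 − 0.85^8.33 = 0.742. For both arms it is 0.742² = 0.55, and for all six grades 0.55^6 = 2.8%. Simulation with random grade counts (20,000 runs) gives:

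| Risk | All six grades have events in both arms: equal mix / peaked mix | Mean number of such grades: equal mix / peaked mix |
|---|---|---|
| 4% | 0% / 0% | 0.5 / 0.6 |
| 10.1% | 0.1% / 0.005% | 2.0 / 1.9 |
| 15% | 1.6% / 0.06% | 3.1 / 2.6 |

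The peaked mix is an assumed 5/15/35/30/10/5% across grades I to VI.

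**The case against.** The strongest reply is that the protocol never shows that guidance changes operating time. It gives no durations and does not describe how the vessel is chosen in the empirical arm, so the net difference is unknown. The term may also mean timing, in which case the intra-operative mechanism falls away. This stands. A reader might infer that the subgroup is certainly biased, or biased in favour of guidance because the table shows ratios below 1. The documents support neither: the direction in the table follows from assuming that guidance lengthens surgery, and with no shift the distortion disappears. What survives is that the variable is post-randomization on either reading and that the text does not say which reading applies.

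A reader might also expect a false treatment-by-duration interaction. The illustration does not show a material one. At a 1 SD shift the long-to-short ratio of risk ratios is only 0.785/0.747 = 1.05 at correlation 0.7, and 0.904/0.887 = 1.02 at correlation 0.3. The distortion is in the effect within each stratum.

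On Suzuki grade, it is fair to say that 21.5 lists levels and does not demand a separate hazard ratio for each, that grouping can be left to the statistical analysis plan, and that outcomes such as CBF or mRS change do not depend on event counts. A few common grades may also yield a very imprecise hazard ratio. It would therefore be too strong to say that the Suzuki subgroups cannot be estimated. Nor does collapsing cure sparsity: two groups would hold on average 3.0/2 = 1.5 to 11.25/2 = 5.6 events each. Other subgroups share the problem, so this part is minor.

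**Conclusion.** The point holds as a caution about one subgroup. Operation time is undefined and post-randomization. If it means duration, it is likely to be affected by allocation, so its subgroup effect is liable to bias of unknown size and direction. The ratios of about 0.93 to 0.98 (0.25 SD shift) down to about 0.75 to 0.90 (1 SD shift) only show the scale under assumed inputs; they are not estimates for this trial. The intention-to-treat comparison of the primary endpoint does not condition on operation time and is unaffected, so the matter is moderate and worth correcting.

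The Suzuki point is secondary. A complete set of six hazard ratios for the primary endpoint is very unlikely: at most about 1.6% in simulation (2.8% by the simpler hand calculation), even at the 15% rate in both arms. It is a sparse-data limitation confined to event outcomes.

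**What to change.** Remove operation time from the treatment-effect subgroups in 21.5. Define it and report it descriptively by arm as a procedural outcome. State that subgroup factors are restricted to values measured before randomization; this would also settle which hypoperfusion reading is meant, since CTP and MRI are scheduled both at screening and after surgery. For Suzuki grade, specify a single ordinal treatment-by-grade interaction or pre-stated collapsed groups, and label the result exploratory, accepting that the estimates will remain imprecise.

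The cost is a change of wording. The trial gives up a subgroup result by operation time and some detail by individual Suzuki grade. No data collection or patient care changes.

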## 21.6. Pre-specified exploratory analyses

- ✧ Blood flow (ASL)
- ✧ Vascular morphology of internal carotid artery and moyamoya vessels

## 21.7. Interim analyses

One interim analysis will be planned and conducted by the Data Monitoring Committee following the accrual and confirmation by adjudication of 50% of planned primary events. The stopping rule of Lan-DeMets approach to O'Brien-Fleming will be adopted for stopping for efficacy or futility. The efficacy stopping boundary at the interim analysis is a 2-sided p-value <0.0015 for the primary endpoint (one-year stroke or death). The final last level of significance with one interim analysis will therefore be 0.0489, with the family wise error rate controlled at 5.00%. The trial would be halted due to futility if nominal critical point (Standardized Z scale) for the primary endpoint crosses the internal boundary for futility ( $\pm 0.595$ ). It will be determined by the executive committee that the trial will be continued or stopped due to the overwhelming efficacy or futility after recommendation of Data Safety Monitoring Board.

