## **6. Study Endpoints**

### **6.1. Primary Endpoint**

All strokes & death within 30 days post-surgery and ipsilateral hemorrhage afterwards

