## 17. Management of Ischemic Events with Temporary Signs during Follow-up

If a patient in either treatment arm develops a potential clinical neurological event (TIA, ischemic stroke), an adjudication packet will be produced by the site within 72 hours. Vascular imaging including angiography will be at the discretion of study neurosurgeon. If primary endpoint occurs, MRI will be performed. Since the most effective therapy is unknown for MMD patients with frequently TIA or recently ischemic stroke, it will be not recommended for patients to receive multimodal neuronavigation bypass or empirical bypass. However, the patient's risk factors should be in target goals.

If patients in the both arms experience TIA or ischemic stroke postoperatively associated with MRI proven infarctions, continued medical therapy alone for them will be recommended by study investigators consisting of neurosurgeons. Decompressive craniectomy will be not recommended to patients without risk of cerebral hernia who have an ischemic stroke.

Additionally, if patients have reached a primary endpoint, that is, stroke in the territory of surgery side, any treatment after occurrence of stroke will be not monitored by investigators and at the discretion of treating physicians.

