### **21.1. Sample size estimates**

Because this trial is a prospective, exploratory, randomized controlled trial, there is no previous data for multimodal neuronavigation guiding precise bypass procedure, the sample size for this trial can't be calculated from the formula. Finally, 100 patients are randomized (1:1) to two groups, 50 of them will undergo direct bypass guided by multimodal neuronavigation, while others will undergo empirical direct bypass procedure.

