### **21.3. Statistical Analyses**

All analyses will be based on the intent-to-treat principle using the FAS, including only events adjudicated by the Clinical Events Adjudication Committee (CEC). The primary hypothesis will be tested using a Cox proportional hazards model with a factor for the treatment group. The time to the first event was used in the model when there were multiple events of the same type. P values and Confidence Intervals (CI) for the Hazard Ratio will be obtained according to the Wald statistic. The following statistics, in addition to HR with CI will be also presented in the summary tables of these analyses: the number of patients with event and Kaplan-Meier estimates of the event rate per treatment group calculated at EoT. Kaplan-Meier estimates of the cumulative proportion of patients with primary endpoint events will be calculated and plotted.

The potential impact of loss to follow-up will be evaluated by the sensitivity analysis.

A Cox proportional hazards model will be used to assess differences between study groups in the rate of primary endpoint under the following three scenarios: (1) all patients will be thought to experience primary endpoint event when the final disposition for the event adjudication is not determined. (2) only patients in the empirical bypass arm will be thought to experience primary endpoint event when the final disposition for the event adjudication is not determined. (3) only patients in the multimodal neuronavigation guiding bypass arm will be thought to experience primary endpoint event when the final disposition for the event adjudication is not determined. These results under the three scenarios will be compared with the result under the scenario in which all patients will be not thought to have primary endpoint event when the final disposition for the event adjudication is not determined. However, the primary analysis result will be reported in patients who are censored not to have the event occurrence when the final disposition for the event adjudication is not determined.

The analysis of and the secondary efficacy variable for the test of multimodal neuronavigation guiding bypass against empirical bypass will comprise the confirmatory analysis. No multiplicity adjustment will be made in all analysis including a confirmatory testing (subgroup analysis).

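### Section 21.7's stopping rule names the wrong primary endpoint, is timed by an event total the protocol never sets, and labels a one-sided 0.0015 as two-sided (two-sided value: 0.0031)

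*Protocol*

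**What the plan says.** Section 21.7 plans one interim analysis, to be done "following the accrual and confirmation by adjudication of 50% of planned primary events". It names the Lan-DeMets version of O'Brien-Fleming for both efficacy and futility and then fixes the levels.

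- Interim: "The efficacy stopping boundary at the interim analysis is a 2-sided p-value <0.0015 for the primary endpoint (one-year stroke or death".
- Final: "The final last level of significance with one interim analysis will therefore be 0.0489, with the family wise error rate controlled at 5.00" per cent.
- Futility: a bound of ±0.595 on the Z scale.
- Decision: "It will be determined by the executive committee that the trial will be continued or stopped", after a recommendation from the DSMB.

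Three other places bear on this rule.

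- Section 6.1 defines the primary endpoint as "All strokes & death within 30 days post-surgery and ipsilateral hemorrhage afterwards". The synopsis and Section 4 agree with it.
- Section 17 describes the endpoint differently: "if patients have reached a primary endpoint, that is, stroke in the territory of surgery side".
- Section 21.1 calls the trial exploratory, says "the sample size for this trial can't be calculated from the formula", and sets 100 patients, 50 per arm, without an event rate, hazard ratio or power.

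**The concern.** A group-sequential rule needs three fixed elements: the events that count, the total that defines the information fraction, and a boundary that belongs to the named spending function at that fraction. In Section 21.7 the first contradicts the endpoint definition, the second is absent, and the third does not reproduce.

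At stake is whether the DSMB and the executive committee can apply the rule as intended. Two people working from this protocol could count different events, could not say when the halfway point is reached, and would use a threshold about half the one the named method gives. The futility bound hangs on the same undefined trigger.

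**Working it through.** **1. Which events count.** The three wordings, applied to the same cases:

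| Event | Section 6.1 | Section 21.7 | Section 17 |
|---|---|---|---|
| Contralateral stroke, day 10 | counts | counts | does not count |
| Ischemic stroke on the operated side, month 6 | does not count | counts | counts |
| Contralateral stroke, month 6 | does not count | counts | does not count |
| Death at month 6, not from ipsilateral hemorrhage | does not count | counts | does not count |

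Sections 6.1 and 21.7 agree up to day 30 and part after it. Section 17 departs from both.

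**2. When the look happens.** The information fraction is t = d / D, with d the adjudicated events so far and D the planned total. The trigger is t = 0.5. The protocol gives no D, and Section 21.1 states no rate, effect size or power from which to derive one. The trigger therefore cannot be computed from this text.

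**3. The boundary.** Inputs: two-sided 5% overall, one look at t = 0.5, Lan-DeMets O'Brien-Fleming spending (all Section 21.7), with 0.025 spent per tail.

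- Interim spending per tail: 2 − 2Φ(z₀.₉₈₇₅/√t) = 2 − 2Φ(2.2414/√0.5) = 2 − 2Φ(3.170) = 0.001525.
- Interim boundary: |Z| = 2.963, one-sided p = 0.0015, two-sided p = 0.00305 (0.0031).
- Final boundary, solved from the bivariate normal with correlation √0.5: |Z| = 1.969, two-sided p = 0.0490.

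The plan's 0.0015 reproduces only as the one-sided value. Its 0.0489 differs from 0.0490 in the last digit only.

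Other readings do not rescue a two-sided 0.0015:

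- Spending 0.05 in total across both tails gives 0.0056 at the interim and 0.0478 at the end.
- Classic O'Brien-Fleming gives 0.0052 and 0.0480.
- A two-sided 0.0015 (|Z| = 3.175) belongs to t = 0.44, where the final level is 0.0495.
- Using 0.0015 at t = 0.5 would leave a final level of 0.0496.

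**4. Family-wise error of the stated pair.** With |Z| > 3.175 at the interim and |Z| > 1.969 at the end (0.0015 and 0.0489), futility not binding:

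| t | 0.1 | 0.4 | 0.5 | 0.6 | 0.9 |
|---|---|---|---|---|---|
| Error | 5.01% | 4.95% | 4.93% | 4.91% | 4.89% |

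For any single look not chosen on the data, the union bound is 0.0015 + 0.0489 = 0.0504, or 5.04%. The corrected pair, 0.00305 and 0.0490, gives 5.00% at t = 0.5.

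**5. What a halfway look could show (assumption).** No primary-endpoint rate is given. As a range I take 4% (Section 3, 30-day stroke per hemisphere), 10.1% (Section 3, one-year death, TIA or stroke) and 15% (Section 15, site-selection ceiling). None of these is a rate for the Section 6.1 endpoint. In 100 patients they give about 4 to 15 events. If that were the planned total, the look would fall at 2 to 7.5, say 2 to 8, events.

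Take the most extreme case, every event in one arm. A Cox Wald statistic is not informative there because the hazard ratio has no finite estimate, so I used two other tests for illustration:

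- Exact binomial, two-sided 2 × 0.5^d: 0.50 at 2 events, 0.0078 at 8.
- Log-rank, 50 at risk per arm: Z = 1.42 at 2 events and 2.94 (p = 0.0033) at 8.
- Log-rank, 25 at risk per arm: Z = 3.06 (p = 0.0022) at 8.

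Only the last passes 0.0031, and none passes 0.0015.

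**The case against.** The strongest reply is that little follows for the error rate. The levels in Section 21.7 are fixed numbers, and step 4 shows that they hold the error at about 5% wherever a single look falls. This stands. A reader might infer that the missing event total undermines the 5% control; the stated levels do not support that. The correct spending boundary does vary with the fraction (two-sided 0.0008 at 40% information, 0.0076 at 60%), but this matters for recomputing a boundary and is not an error of the stated rule.

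A reader might also infer that the executive committee would pick the moment after seeing data. The documents do not support this either: the committee acts on a DSMB recommendation, and Section 22 requires a charter and guidelines before the trial starts.

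Section 21 refers details to a SAP that is not shown, which could contain an event total. The point on timing is therefore limited to this protocol. Even so, Section 21.7 relies on a planned number while Section 21.1 says the calculation behind one could not be made, and the two need reconciling. The endpoint and boundary errors do not depend on the SAP.

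Two further inferences should be resisted. One is that ±0.595 reveals a hidden event-driven design with a particular power: the protocol states no power, so this is conjecture. The other is that the primary test must change. Section 21.3 says "P values and Confidence Intervals (CI) for the Hazard Ratio will be obtained according to the Wald statistic", and nothing in this point shows that choice to be wrong.

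Finally, the synopsis and Sections 4 and 6.1 agree with each other, so the endpoint itself is settled. The fault lies in the bracket in Section 21.7 and in the Section 17 wording.

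**Conclusion.** The point holds on three counts: a wrong endpoint in Section 21.7, a trigger that cannot be carried out from this protocol, and an interim level whose label does not fit the named method.

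The numerical error is a factor of two in the interim level (0.0015 against 0.0031; |Z| 3.175 against 2.963) and errs on the strict side: 4.93% is spent instead of 5.00%. That 0.0015 is a mislabelled one-sided value is an inference from the match. The corrected figures assume 0.025 spent per tail and a look at exactly 50% information.

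The damage is to the usability and correctness of the stopping rule, not to type I error. Under the assumed 4 to 15 events, an efficacy stop at a halfway look would be practically unreachable. This illustrates scale only, since the protocol gives no primary-endpoint rate.

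**What to change.** Choose one of two routes.

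(a) Keep the look. In Section 21.7, replace the bracketed endpoint with the Section 6.1 definition. State the planned number of primary events that defines 50%. Write the interim boundary as two-sided p<0.0031 (|Z|>2.963) with final level 0.0490, and say that the boundary is recomputed from the spending function at the observed fraction of the planned total. The cost is more than wording: an event total is needed, and Section 21.1 currently offers no basis for one. The final level moves only from 0.0489 to 0.0490.

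(b) Delete the formal efficacy and futility look, keep the DSMB safety review in Section 22, and test the final analysis at two-sided 0.05. This fits the exploratory design in Section 21.1 and is mainly a deletion. The sentences on stopping early in Section 21.8 and on stopping for efficacy in Section 22 would need to be brought into line. The price is that there is no formal early stop for efficacy or futility.

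Under either route, reconcile the description of the primary endpoint in Section 17 with Section 6.1. The analysis method in Section 21.3 can stay as it is.

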#### Risk of Stroke or Hemorrhage for MMD

The greatest concern for MMD is the risk of subsequent stroke or hemorrhage even with surgical revascularization and regular medical therapy. A retrospective, single-center, cohort study showed most subsequent ischemic events appeared in the first 2 years after surgery. The Kaplan-Meier estimated stroke risk was 10.1% and 12.7% in the first 2 years and 5 years after surgery for all patients treated with surgical revascularization, approximated 10.1% incidence of mortality or TIA or stroke at 1 year after surgery in 802 patients with the MMD. Incidence of rebleeding range from 12.5~20% of patients with onset hemorrhage symptom who underwent revascularization surgery, while with the conservation treatment the rebleeding estimated occurrence of 6.8–65%.

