### **Surgical treatment for MMD**

Revascularization surgery has played an important role for treatment of MMD. Several general methods of revascularization had been used: direct, indirect and combined techniques. Two large studies with long term follow-up showed a good safety profile for surgical treatment. During the postoperative 30 days the risk of stroke is highest (approximately 4% per hemisphere); and after the first month, the risk decreases fairly. It is reported that patients have a 96% probability of remaining stroke-free over the subsequent 5 years. Patients with MMD have a higher risk of perioperative ischemic events. The complications associated with the treatment include stroke, infection, and intracranial hemorrhage.

Currently, there are no reports on the MMD research that refer to the criteria of receptor vessel selection in bypass surgery for MMD. Surgeons usually performed superficial temporal artery to MCA (STA–MCA) anastomosis. Sometimes when patients have severe ischemia in ACA area the STA can also be anastomosed to the branch of the ACA. So precisely choosing receptor vessel remains uncertain. As the imaging advanced, ASL can be used as a perfusion method to detect the ischemia area and intraoperative ICG angiography using Flow800 software can be used to reflect the lower flow velocity and superficial perfusion. Guided by this two imaging data, we try to precisely find the receptor vessel.

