## **15. Leading Phase of Trial for Site Selection**

Candidate sites for trial will be initially identified based on hospital grades, the intervention experience, and the volume of revascularization surgery cases. It will take three months before the trial kickoff for the steering committee to assess site research capability and commitment to the study. The center meeting the following criteria will be enrolled into the trial: ① at least 5 cases will be recruited within the leading phase; ② the rate of perioperative complications should be not more than 15% (stroke or death).

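### With 100 patients the half-way look would fall at about 2 to 5 events (8 at most), too few for the efficacy boundary to be reached or for the futility rule to tell benefit from none

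*Protocol*

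**What the plan says.** Protocol 21.7 has one interim analysis, triggered "following the accrual and confirmation by adjudication of 50% of planned primary events". It uses Lan-DeMets spending of O'Brien-Fleming type, and "The efficacy stopping boundary at the interim analysis is a 2-sided p-value <0.0015 for the primary endpoint". The final level is 0.0489. The trial would be halted for futility if Z falls inside ±0.595. The executive committee decides, after a recommendation from the monitoring board.

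Section 21.1 gives no event target. It calls the trial exploratory, says that "the sample size for this trial can't be calculated from the formula", and fixes the size: "100 patients are randomized (1:1) to two groups". Section 21.3 tests the primary hypothesis with the Wald statistic from a Cox model.

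The protocol gives three rates that bear on the number of events:
- Section 3, on surgical treatment: in the 30 days after operation "the risk of stroke is highest (approximately 4% per hemisphere".
- Section 3, on risk of stroke or hemorrhage: "approximated 10.1% incidence of mortality or TIA or stroke at 1 year after surgery". This includes TIA, which is not part of the primary endpoint.
- Section 15: for a site to be selected, "the rate of perioperative complications should be not more than 15% (stroke or death". This is a ceiling, not an expected rate.

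**The concern.** The timing fraction, the efficacy boundary and the futility band are fixed in the protocol, so they are not left to the SAP. An SAP could supply the missing event number, but it could not draw many more events from 100 patients. If half of the realistic total is a handful of events, the early efficacy stop exists only on paper, and the futility rule acts on whether one patient's event fell in one arm or the other. A trial described as exploratory could then end early on almost no information, before enrolment and 12-month follow-up of blood flow, mRS, NIHSS and Barthel score are complete.

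**Working it through.** **1. The plan's own boundaries.** O'Brien-Fleming-type spending of 0.025 per side at half information spends 2 × [1 − Φ(2.241/√0.5)] = 0.00153 per side, so |Z| > 2.963 and two-sided p < 0.0031. The final level is 0.0490. The stated 0.0015 is therefore the one-sided value labelled two-sided; as written it requires |Z| > 3.17. With 0.0489 at the end, the overall error is 4.93%, so the slip is conservative. Both boundaries are used below.

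**2. Events at the look.** The assumptions are that planned events equal the expected total and that each patient contributes one operated hemisphere. Events at the look = 100 × rate / 2.
- 4%: 4 events, half is 2.
- 10.1%: 10.1 events, half is about 5.
- 15%: 15 events, half is 7.5.

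If the new arm truly has half the control risk, the total is 50 × rate + 50 × rate/2 = 75 × rate, and the look falls at 1.5, 3.8 or 5.6 events.

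**3. Reach of the efficacy boundary.** With D events split a:b between equal arms, the log-rank Z is about (a − b)/√D, which is at most √D. At D = 8 this is 2.83. Allowing for the shrinking risk set (50 per arm, everyone followed) raises it to 2.94, still below both 2.963 and 3.17. On the √D formula, crossing 3.17 needs 11 interim events all in one arm, and crossing 2.963 needs 9. That implies 22 or 18 planned events, a risk of 22% or 18%, above the 15% ceiling.

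The Wald statistic is about ln(a/b)/√(1/a + 1/b). Its largest finite value at 8 events is for 7:1: 1.946/√(1/7 + 1) = 1.82. Exceeding 3.17 takes at least 23 events. If all events fall in one arm, the hazard ratio estimate is not finite and the Wald Z tends to 0, so the most extreme split could be read as futile.

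**4. What triggers futility.** A 1:1 split gives Z = 0, 2:1 gives 1/√3 = 0.58, 3:2 gives 1/√5 = 0.45 and 4:3 gives 1/√7 = 0.38; all are inside 0.595. A 3:1 split gives 1.00, 4:2 gives 0.82 and 5:3 gives 0.71; all are outside. So at even counts only a tie triggers the rule, and at 3, 5 or 7 events a difference of one event does.

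**5. How often it is met, given that the look is reached.** A hazard ratio of 0.5 is assumed, since the protocol gives no effect size. Normal approximation: Z has mean (√D/2) × ln 2 and variance 1. Exact counting: each event falls in the control arm with probability 2/3. Log-rank simulation: 50 per arm, simultaneous entry.

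| D | √D | Largest finite Wald Z | Normal, HR 0.5 | Exact, HR 0.5 | Log-rank, HR 0.5 | Log-rank, HR 1 |
|---|---|---|---|---|---|---|
| 2 | 1.41 | 0.00 | 40% | 44% | 45% | 51% |
| 3 | 1.73 | 0.57 | 38% | 67% | 45% | 51% |
| 4 | 2.00 | 0.95 | 36% | 30% | 30% | 38% |
| 5 | 2.24 | 1.24 | 34% | 49% | 50% | 64% |
| 6 | 2.45 | 1.47 | 33% | 22% | 23% | 32% |
| 7 | 2.65 | 1.66 | 31% | 38% | 39% | 57% |
| 8 | 2.83 | 1.82 | 29% | 17% | 18% | 29% |

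Under no effect the normal approximation is 2Φ(0.595) − 1 = 45% at every D. The methods part at D = 3 because a 2:1 split lies almost on the line.

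**6. Effect on the primary test.** By simulation at control risks of 5% to 15% and hazard ratio 0.5, final power is about 7% to 20%. Treating the futility rule as binding lowers it by about 0 to 3 percentage points.

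**The case against.** An O'Brien-Fleming boundary is meant to be almost inactive early and costs hardly any alpha (0.0489 against 0.05), so one that rarely acts is no defect in itself. The weak separation comes mainly from 100 patients and rare events, and deleting 21.7 does not cure that. Nearly all trials that the rule would stop would have finished non-significant anyway. Stating a planned event number, or making futility advisory, would be a smaller change. Much of this stands, but it does not make the stated efficacy stop attainable or the futility rule informative.

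Some stronger readings are not supported:
- A reader might infer a firm wrong-stop probability. It depends on the method and on odd or even counts; simulation with staggered entry gives 27% to 44%. It is also conditional: at 5% control risk and a look at 3 events, only about 72% of trials reach the look, so about 0.45 × 72% = 32% of all trials meet the rule.
- A reader might take 8 events as what the protocol expects. That figure rests on the site-selection ceiling; the other two rates give about 2 to 5.
- A reader might infer an automatic stop. The executive committee decides.
- A reader might infer that data on enrolled patients are lost. Section 21.8 calls unfinished patients to an end-of-trial visit, and section 16 includes the neurological scales, CTP and MR there. What is curtailed is further enrolment and the remaining scheduled follow-up.

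**Conclusion.** The point holds as a design weakness of moderate weight. At about 2 to 5 events, and still at about 8, the efficacy boundary is effectively unattainable, whether 3.17 or 2.96 is used and whether the statistic is log-rank or Wald. The futility rule is decided by one or two patients and barely separates a halved risk from no effect: roughly 30% to 40% against about 45% by normal approximation, with 18% to 50% by log-rank simulation and 17% to 67% by exact counting under the halved risk.

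This rests on two assumptions that the protocol does not settle: that planned events equal the expected total, and a hazard ratio of 0.5. Section 21.1 itself says "there is no previous data for multimodal neuronavigation guiding precise bypass procedure". A reader might infer a serious loss of power for the primary comparison, but the loss is about 0 to 3 points because power is already low. The harm is a possible early end to an exploratory trial on very little information.

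**What to change.** Delete the efficacy and futility stopping rules from 21.7 and test the primary endpoint once, at the end, at two-sided 0.05. Keep the safety review in Section 22, where the monitoring board meets about every three months and may already recommend termination if an arm is unsafe. Align that section's wording on termination for efficacy with the change.

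At minimum, remove the futility halt and state that no early efficacy stop is attainable at the expected number of events. Correcting only the boundary value or supplying an event number would not help unless that number were well above what 100 patients can be expected to yield.

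The cost is a protocol amendment and matching text in the monitoring board charter. The downside is that no early futility stop remains, so patients who might have been spared enrolment would still be recruited.
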